4.2.2. Secondary objectives

[figure not shown]
- To determine whether there is a difference in quality of life between the two treatments.
- To determine whether there is a difference in healing, complications and adverse events between the two treatments.
- To determine whether there is a difference between return to work, driving and usual activities between the two treatments
- To determine which is the most cost-effective treatment option if provided in the NHS.
- To explore patient experiences and the psychological and social impact of their treatment.

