7.2. Secondary outcome measures

7.2.1. Functional data

Functional data including range of movement (dorsiflexion, plantarflexion, inversion, eversion (degree angles)), circumferential swelling and weight-bearing status at four weeks post baseline. Range of motion will be assessed using a goniometer. Weight-bearing will be classified as touch weight-bearing, partial weight-bearing or full weight-bearing. Circumferential swelling of the injured ankle will be measured using a tape measure. Circumference of the non-injured ankle will be measured in the same way and used as a comparison. Range of movement assessments and circumferential measurements must be conducted by a physiotherapist trained in the requirements of the study protocol and recorded in the patient's medical record.

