7.2.5. Return to usual activities

At baseline, patients will be asked for their employment status prior to injury (unemployed, homemaker, volunteer, full time education, part-time paid employment, full time paid employment). At 10 weeks participants will be asked for their current employment status and will be asked whether their ankle injury has an impact on every day activities (0 to 10 scale anchored by no effect on daily activities and completely prevented daily activities).

Absenteeism (days off work), presenteeism (feeling less productive at work), and time off usual social activities, are productivity losses that we will measure at 4 and 10 weeks, by questions included in the resource use questionnaire. Participants will also be asked if they drove pre-injury, whether they had started driving again, and the date they resumed driving.

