The profiles from the patients’ answers to the EQ-5D-5L will be weighted using the EuroQol’s published United Kingdom societal utility tariffs to produce a composite, utility based quality of life score and EuroQol has piloted the 5L valuation scores²⁵. If final scores are not available by the end of the trial, the crosswalk developed by EuroQol from the three level scores will be used. Quality Adjusted Life Years will then be created from the four time point utility scores assuming a linear change between the time points and using the area under the curve approach. Incremental QALY gains between arms will then be estimated using regression analysis adjusted for baseline utility and site, age and fracture complexity variables.

Multiple regression will be used to investigate differences between the two groups in the other continuous outcomes measured at four weeks post-baseline (e.g. degrees of range of movement (dorsiflexion, plantarflexion, inversion, eversion), circumferential swelling and 10 weeks (e.g. return to daily activities on 0-10 scale). Complications in the two groups (presence and severity), healing status (displaced / undisplaced and evidence of post-operative fracture healing (yes/no)), employment status at 10 weeks, driving status and weight bearing status will be investigated using logistic regression (binomial or multinomial depending on the number of categories), again taking study site, age and fracture complexity into account. Survival analysis will be used to investigate the time from randomisation to starting to drive again. Supplementary analysis (b) to (e) as described for the primary outcome will also be conducted for secondary outcomes.)

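### Return to work is analysed as employment status at week 10 without using pre-injury employment, so the comparison is diluted and does not estimate return to work

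*Protocol*

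**What the plan says.** Section 4.2.2 lists as a secondary objective: "To determine whether there is a difference between return to work, driving and usual activities between the two treatments".

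Section 7.2.5 describes the data. On the baseline item it states: "patients will be asked for their employment status prior to injury (unemployed, homemaker, volunteer, full time education, part-time paid employment, full time paid employment"). For follow-up, "At 10 weeks participants will be asked for their current employment status". The same section records absenteeism, presenteeism and time off social activities at 4 and 10 weeks through the resource use questionnaire, and a 0 to 10 rating of impact on daily activities.

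Section 12.2.3 fixes the analysis: "employment status at 10 weeks, driving status and weight bearing status will be investigated using logistic regression (binomial or multinomial"). The choice between the two forms rests on how many categories there are, and the model is fitted "again taking study site, age and fracture complexity into account". No other effectiveness analysis of work is named. Pre-injury employment appears in three other places:

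- the baseline table (12.2.1);
- possibly supplementary analysis (d) of 12.2.2, which adds baseline variables that differ by chance and is extended to secondary outcomes;
- the economic evaluation (12.4), where productivity estimates are adjusted for work status before randomisation.

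**The concern.** Returning to work is a change from a person's own starting point, but the named outcome is a category at one time. This raises two problems.

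1. Someone unemployed or a homemaker before injury cannot return to work. That person carries no information on the objective, yet enters the model on the same footing as an employee.
2. As listed, the categories describe the type of employment. A full-time employee still signed off sick could give the same answer as one who is back, so an earlier return need not move the outcome.

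Section 12.1 records that patients named getting back to work among their most important issues. A null result on employment status could be reported as no effect on return to work when the analysis was poorly placed to see one.

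**Working it through.** **The plan's own figure.** Section 12.1 gives a difference of 10, SD 21.9, two-sided 0.05 and 90% power. The t-test calculation gives 101.76, so 102 per arm and 204 in total, as stated. I use 102 per arm below. The protocol gives no power for the categorical secondary outcomes.

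**Objective against model.**

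| Element | Objective (4.2.2) | Model (12.2.3) |
|---|---|---|
| Population | People with work to return to | All participants |
| Outcome | Back at work | Employment category at week 10 |
| Starting point | Pre-injury work | Not used |

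**Cost of ignoring pre-injury status.** The protocol does not give the share working before injury or the return rates, so these are assumptions: a share *w* of 50 to 80% working, with return by week 10 of 50% in one arm and 70% in the other among them. Nobody who was not working before injury is working at week 10. The outcome is simplified to working or not, tested by an unadjusted comparison of two proportions.

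- All participants: proportions 0.5*w* and 0.7*w*, with 102 per arm.
- Prior workers only: proportions 0.5 and 0.7, with about 102*w* per arm.
- Power ≈ Φ[(Δ − 1.96·SE₀)/SE₁], where SE₀ = √(2·p̄(1−p̄)/n) and SE₁ = √((p₁(1−p₁)+p₂(1−p₂))/n).

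For *w* = 0.5:

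- All participants: 0.25 v 0.35, n = 102, SE₀ = 0.0642, SE₁ = 0.0638. Power = Φ[(0.10 − 0.1258)/0.0638] = 34%.
- Prior workers: 0.50 v 0.70, n = 51, SE₀ = 0.0970, SE₁ = 0.0950. Power = Φ[(0.20 − 0.1901)/0.0950] = 54%.

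Simulation (4,000 trials per row) agrees with the formula to within about 3 points across the four rows:

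| Working before injury | Power, status ignored | Power, prior workers only | Loss |
|---|---|---|---|
| 50% | 35% | 55% | 20 |
| 60% | 43% | 62% | 19 |
| 70% | 55% | 70% | 15 |
| 80% | 65% | 75% | 10 |

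These rows assume that the week-10 item does detect being back at work. If sick leave is hidden inside a category, the loss is larger.

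**Two lesser points in the same section.**

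*Weight-bearing.* Section 7.2.1 states: "Weight-bearing will be classified as touch weight-bearing, partial weight-bearing or full weight-bearing". This is an ordered scale, but 12.2.3 chooses binomial or multinomial by the number of categories. With 102 per arm, an assumed control split of 15/40/45% and a common odds ratio, simulated power (2-df multinomial test v 1-df ordinal test, both unadjusted) is:

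- 48% v 58% at odds ratio 1.8;
- 74% v 82% at 2.2;
- 84% v 91% at 2.5.

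A 20/40/40% split gives 49% v 59% at 1.8. Under no effect both tests reject 4.5% of the time, so the multinomial test is valid.

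*Complications.* The only rate in the protocol is 6.6%, for wound infection in a cited study (section 3). I simulated the adjusted logistic model at 204 participants, assuming three equal sites, 40% comminuted fractures and no treatment effect. There is no finite estimate in 3.5% of trials at a 6.6% rate, 12% at 5%, 64% at 2% and 93% at 1%. Rates other than 6.6% are assumptions.

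**The case against.** Several points on the other side have force.

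- *Randomisation protects the comparison.* Correct. Leaving out pre-injury employment does not bias the arm difference; it dilutes it and changes what is estimated.
- *Baseline employment is already used.* Supplementary analysis (d) could bring it in, but only if the arms happen to differ, and only as a supplementary result. The costing adjustment does not reach the effectiveness analysis.
- *Absenteeism may already be covered.* Section 7.2.5 sits under secondary outcome measures, and 12.2.3 introduces its continuous outcomes as examples. Days off work could fall within that list. This stands: one cannot say absenteeism is reserved for costing, only that no effectiveness analysis of it is named.
- *Work is partly captured elsewhere.* The ankle score contains an item on activity compared with before injury, and the daily-activities rating is analysed. Both help, but one is a single item in a composite and the other is not specific to work.
- *The week-10 questionnaire is not shown.* Also correct. The point about sick leave depends on its wording.
- *The SAP will supply detail.* It may, but the outcome and its covariates are already fixed in 12.2.3.

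A reader might infer that the categorical secondary analyses in general do not answer their questions. The protocol does not support that. Healing outcomes are binary and suitably modelled. Driving also has a time-to-event analysis. Multinomial regression of an ordered scale is valid and does not need proportional odds. Nor does the text require a separate model for each of the ten complications: presence can be read as any complication, and failure to estimate is uncommon at the one cited rate.

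**Conclusion.** The point holds for return to work. The objective asks who got back to work. The named analysis compares employment categories in everyone, without the pre-injury status that the trial collects.

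The consequence is dilution and a mismatched estimand, not bias. The size is about 10 to 20 power points at 204 evaluable participants. It rests on assumed return of 50% v 70%, on 50 to 80% working before injury, and on a simplified working-or-not outcome. That the categories hide sick leave is likely from the list in 7.2.5, but unconfirmed without the week-10 item.

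The ordinal and sparse-event points are optional refinements. The first is worth about 7 to 10 power points if odds are proportional. The second matters only for types much rarer than the cited 6.6%.

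**What to change.** In section 12.2.3, or in the SAP with a matching protocol amendment:

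1. Define the return-to-work outcome as back at work by week 10, among participants in part-time or full-time paid work before injury. Derive it from the absenteeism and employment items already collected, once the sponsor confirms that they identify who is back.
2. Analyse it by logistic regression adjusted for site, age, fracture complexity and pre-injury full-time or part-time status.
3. Name days absent at 4 and 10 weeks as an analysed secondary outcome in the same group.

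The cost is wording, plus a smaller analysis set for this one outcome. If the existing items cannot identify who is back at work, the week-10 questionnaire would need one further question.

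Optional: use proportional-odds regression for weight-bearing, with a check of the assumption. Make any complication the main complication model, and report very rare types as counts with exact confidence intervals.

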12.3. Qualitative Component

At approximately ten weeks post-baseline, telephone interviews will be carried out with up to 20 participants or until data saturation. A maximum variation strategy will be used to capture a range of experiences of participants receiving each treatment. Telephone interviews will last up to 60 minutes, will be recorded digitally, and were chosen to reduce costs and for convenience to the patients. The topic guide has been developed through collaboration with service users, and addresses:

- Experiences of each type of treatment (plaster/boot).
- Lifestyle implications – individual (e.g. washing), family (including caregivers, as requested by feedback from patient and public involvement), social, psychological, work, financial, residential, transport (e.g. driving), diet, leisure activities, and independence.
- Expectations, mind-set, confidence, including the perceived views of their carers as suggested by the patient and public involvement.

The telephone interviews will be transcribed verbatim, anonymised, and coded using Thematic Analysis²⁶. A second researcher will analyse a selection of transcripts to validate the codebook/coding. It is anticipated that the findings from this qualitative study will enhance the results by explaining the psychological and social impact of each treatment.

12.4. Economic Evaluation

The primary economic evaluation will compare the costs and health benefits of the support boot compared to plaster in short-term ankle fracture management from an NHS and Personal Social Services perspective. In sensitivity analysis, an economic evaluation from a societal perspective on costs will be performed.

The evaluation will be:

1. A cost-utility analysis at ten weeks post-randomisation; Quality Adjusted Life Years (QALYs) between arms will be compared to identify whether any treatment arm is dominant (i.e. less costly and more effective). If no arm is dominant, results will be presented as a bootstrapped incremental cost-effectiveness ratio (ICERs) with respect to QALYs gained. Bootstrapped estimates of costs and effects will be plotted in the cost-effectiveness plane. Incremental net monetary benefit statistics (INMB) will be derived using the £20,000 and £30,000 societal willingness to pay thresholds for a QALY. Cost-Effectiveness Acceptability Curves (CEACs) will be plotted to show the probability of the intervention being cost-effective at a range of societal willingness to pay thresholds, thus addressing uncertainty around the adoption decision. If one arm is dominant, ICERs are not meaningful and we will only report INMB statistics and plot the cost-effectiveness planes and CEAC.
2. A cost-effectiveness analysis at approximately 5 weeks post-baseline, coinciding with the collection of primary clinical outcome; Costs and Olerud and Molander scores between arms will be compared to identify whether any treatment arm is dominant. If no arm is dominant, results will be presented as a bootstrapped incremental cost-effectiveness ratio with respect to the Olerud and Molander¹⁴ scale. If the treatment arm is a dominant or dominated strategy, ICERs will be

negative and not meaningful. In that case, we will only report INMB statistics in relation to QALYs and will not proceed any further with the cost-effectiveness analysis with respect to the Olerud and Molander scale.

Collecting 5 week and 10 week resource use:

Resource use collection will take place as defined in above section “7.4 Resource Use” in this protocol.

At 10 weeks, resource use for the primary economic result will result from adding secondary care resource use collected from the review of 10 weeks of medical notes and the two resource use questionnaires at 4 weeks and 10 weeks.

For the second economic result, the primary clinical outcome collected at approximately 5 weeks (4 weeks + 3-10 days) after randomisation will be compared with costs for the same period. We will identify the proportion of secondary care cost, collected from medical notes, taking place in the additional days post the 4 week clinic visit for the patient, and assume the patient would have an equal proportion of cost for the other cost categories, collected by questionnaire. This assumed incremental patient reported cost, will be added to the 4 week cost data collected from questionnaires and the corresponding period cost from medical notes, to compose a total patient cost from baseline to collection of primary clinical outcome data.

Valuing resources:

Resource use will be valued using unit costs for health and social care, department of health reference costs or other national routine sources²⁷⁻³⁰ whenever available. Trust finance departments will be contacted for procurement costs on the boot and plaster materials. Productivity losses will measure absenteeism and presenteeism and be valued using the human capital approach³¹⁻³² in the main analysis, and the friction costs approach in sensitivity analysis. Estimations will be adjusted for pre-randomisation work status and return to work.

Analysis of costs and outcomes:

Costs and QALYs (mean and confidence intervals) will be estimated using regression analysis, adjusting for site, age, and fracture complexity in addition to baseline utility for QALYs). We will ascertain whether the treatment arm would be dominant, i.e. less costly and more effective, or dominated, i.e. more costly and less effective, with respect to QALYs and the Olerud and Molander scale.

Missing data in the economic result:

Cost is cumulative and additive: missing data in one cost component at one follow-up time point means that the full cost per patient cannot be computed. A specific missing data strategy has been developed for the economic evaluation, in case of poor patient-completion of resource use questions.

Missing data will be imputed using multiple imputation methods, in a two-stage ordinary least squares model, adjusting for socio-demographic characteristics

collected at baseline. As the primary economic result are parameters (ICERs / NMB) relating Costs and QALYs, the imputation models will simultaneously include disaggregated cost categories and utilities.

If less than 30% of the cost and QALY data is missing, the main economic analyses will report the complete case scenario. If more than 30% of data is missing, the main economic analysis will report the primary economic result using the completed imputed dataset, with the complete case scenario as the secondary analysis. Should the secondary analysis using the primary clinical outcome require imputation, imputed value sets from the statistical analysis will be used to estimate the economic result parameters.

Sensitivity analysis:

One way and scenario sensitivity analysis will be used to address uncertainty of costing and methodological assumptions. These may include, for example, adding a societal perspective to the primary NHS+PSS (prescribed specialised services) result, valuing productivity losses using a different approach (i.e. friction cost), and costing assumptions for the 3 to 10 days incremental cost period not directly captured in questionnaires. Results will be presented disaggregated by perspective (i.e. National Health Service/patients/societal) for clear decision-making information.

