At Poole Hospital, fitting patients with a plaster following open reduction and surgical internal fixation costs approximately £20.84 for materials plus plaster technician labour costs for 10-15 minutes per case. Although there are a range of boots available on the market at varying prices, those used are chosen for their quality and value for money – for example, the pneumatic walker boot currently in use at Poole Hospital costs £52.39 and we expect it may be equally labour intensive (information provided by plaster technicians).

However, the boot may be more comfortable as it can be removed at night and for washing, and ultimately improves patient satisfaction⁸. Despite boots having fewer limitations than plaster, they can still be considered cumbersome and disposal of plasters and boots both have environmental impact.

Furthermore, some studies report conflicting and inconclusive findings with regards to complications. Lehtonen et al⁹ found wound infections in 6.6% of those who mobilised early and a high incidence of deep vein thrombosis. On the other hand, Vioreanu et al⁶ found patients who exercised once primary wound healing had taken place had fewer wound infections and the immobilised group had problems with deep vein thrombosis. Farsetti et al¹⁰ compared two case series of 22 patients and found no correlation between wound complications and continuous passive movement applied for the first three weeks post-operatively.

Although there are two current trials underway, one in London¹¹, the other in Toronto¹², the London study is a smaller study (n=76) and does not encourage active movement through range of movement exercises whilst the Toronto study is unrealistic not allowing weight-bearing in plaster. The most recent systematic review by Thomas et al³ (p 674) and a Cochrane report by Lin et al¹³ (p 431), both recommend the need for more research with well-designed and conducted trials with adequate numbers and reporting. There is limited evidence supporting the use of a removable type of immobilisation and active range of movement and no previous studies, to the research team's knowledge, have investigated the socio-economic factors and psychological impact which may be related to return to function, independence, and work.

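### The 5-week cost versus ankle-score analysis stops whenever one arm is dominant, although dominance is a reason to omit only the ICER

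*Protocol*

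**What the plan says.** Section 12.4 of the protocol sets out two economic analyses. The second is "A cost-effectiveness analysis at approximately 5 weeks post-baseline, coinciding with the collection of primary clinical outcome". Its reporting has two branches:

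- No dominance: "If no arm is dominant, results will be presented as a bootstrapped incremental cost-effectiveness ratio with respect to the Olerud and Molander" scale.
- Dominance either way: the trigger is "If the treatment arm is a dominant or dominated strategy, ICERs will be" negative and therefore uninterpretable. The consequence is "In that case, we will only report INMB statistics in relation to QALYs and will not proceed any further with the cost-effectiveness analysis" on the ankle-score scale.

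Under the sub-heading on analysis of costs and outcomes, the same section says what dominance means: "dominant, i.e. less costly and more effective, or dominated, i.e. more costly and less effective, with respect to QALYs and the Olerud and Molander scale". No confidence interval, test or bootstrap proportion enters the definition.

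Item 1, the 10-week cost-utility analysis, meets the same situation differently: "If one arm is dominant, ICERs are not meaningful and we will only report INMB statistics and plot the cost-effectiveness planes and CEAC".

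**The concern.** The reason given for stopping is that the ICER would be negative. That is a sound reason not to print the ratio. The incremental cost, the incremental ankle score and their joint distribution stay well defined and interpretable whatever their signs, and item 1 proceeds on that basis. The protocol gives no reason for treating item 2 differently.

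Two things are at stake:

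- **Imprecision.** An arm can be cheaper and better on its point estimates while the cost difference is very imprecise. If the analysis ends there, the reader learns that the boot dominates, or is dominated, at the primary time point, but not how secure that statement is.
- **Assumed costs.** Part of the 5-week cost is not observed. Section 12.4 takes the patient-reported cost for the 3-10 days after the 4-week visit to be proportional to the secondary-care cost in those days. It names this costing as a candidate for sensitivity analysis. If work stops once the base case shows dominance, nobody checks on the ankle-score scale whether the sign that triggered the stop depends on that assumption.

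**Working it through.** **The two items side by side, when one arm is dominant**

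| | Item 1 (QALYs, 10 weeks) | Item 2 (ankle score, about 5 weeks) |
|---|---|---|
| ICER | omitted | omitted |
| Net monetary benefit | reported | only the QALY-based figure |
| Cost-effectiveness plane | plotted | none stated |
| Acceptability curve | plotted | none stated |
| Analysis continues | yes | no |

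**How often the rule could fire**

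Inputs from the protocol:
- Section 12.1: 102 evaluable per arm, SD 21.9, difference 10 points, two-sided 0.05, 90% power.
- Section 3: plaster materials £20.84; "the pneumatic walker boot currently in use at Poole Hospital costs £52.39". The difference in materials is 52.39 − 20.84 = £31.55.

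Assumptions that are not in the protocol:
- SD of total cost per patient of £200 to £1,000, equal in both arms.
- True cost difference of −£31.55, 0 or +£31.55. Section 3 has the boot dearer on materials; the negative value stands for savings elsewhere.
- Cost and score differences normally distributed, uncorrelated and unadjusted.
- Dominance judged on the observed means.

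Step 1, the protocol's sample size. The normal approximation gives 2 × (1.960 + 1.282)² × 21.9² / 10² = 100.8, so 101 per arm. The exact t calculation gives 102 per arm with power 0.9007. The stated 204 is reproduced.

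Step 2, ankle score. SE = 21.9 × √(2/102) = 3.07. With a true 10-point benefit, P(observed difference favours the boot) = Φ(10/3.07) = Φ(3.26) = 0.9994. The trigger then turns almost wholly on the sign of the cost difference.

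Step 3, cost. SE = SD × √(2/102).

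Step 4, the rule fires when the boot is cheaper and better, or dearer and worse: P = P(score up) × P(cost down) + P(score down) × P(cost up).

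| Assumed cost SD | SE of cost difference | 31.55/SE | Boot truly £31.55 cheaper | No true cost difference | Boot truly £31.55 dearer |
|---|---|---|---|---|---|
| £200 | £28.0 | 1.13 | 87% | 50% | 13% |
| £500 | £70.0 | 0.45 | 67% | 50% | 33% |
| £1,000 | £140.0 | 0.23 | 59% | 50% | 41% |

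Step 5, no true difference in cost or score. The rule fires in 50% of trials if the two estimated differences are uncorrelated, and in 33% to 67% for a correlation of +0.5 to −0.5.

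Step 6, how secure that dominance would be. The 95% half-width on the cost difference is 1.96 × SE: £55, £137 and £274 for the three SDs, against a materials difference of £31.55. In the most favourable cell (SD £200, boot £31.55 cheaper) the boot is dominant on observed means in 87% of trials. Both differences are significant in that direction in only Φ(3.26 − 1.96) × Φ(1.13 − 1.96) = 18%. At SD £1,000 the figures are 59% and 4%.

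**The case against.** Much of the case for the plan stands.

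- **Item 2 withdraws no plane or curve.** A reader might infer from the contrast with item 1 that dominance removes a planned plane and acceptability curve. The protocol does not support that: the only output item 2 names is the bootstrapped ICER. A plane on the ankle score would be an addition.
- **Uncertainty is not hidden altogether.** Section 12.4 plans means and intervals for costs and QALYs with no dominance condition, although it does not say explicitly that the 5-week cost gets its own interval. The 5-week ankle-score difference is the primary outcome (section 12.2.2) and is reported regardless. Item 1 keeps its plane and curve. Only the joint result is missing.
- **This is not selective reporting in favour of one arm.** The rule is pre-specified and symmetric, cost and score are compared in every case, and finding dominance is itself a result.
- **Point estimates are an inference.** The protocol defines dominance by direction and does not say how direction is established; an analysis plan might. It remains the natural reading, because a negative ICER is a matter of the signs of the estimates.
- **Falling back on QALYs has a plausible motive.** Thresholds are given for a QALY (£20,000 and £30,000) but not for an ankle-score point.

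None of this explains why the joint result should end with the ratio. Item 1 shows that it need not.

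**Conclusion.** The point holds as a limited one. Followed as written, item 2 lets the sign of a possibly very imprecise cost difference end the cost versus ankle-score analysis at the primary time point. No joint uncertainty is then shown, and the assumed 3-10 day costs go untested on that scale.

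The chance of this is about 13% to 87% over the assumed range. It rests on a cost SD that the protocol does not give, on a materials-only cost difference taken in either direction, on a true 10-point benefit and on no correlation between cost and score. A reader might conclude that reporting is close to a coin toss. That is right with no true cost difference, or roughly so at the larger SDs, but it does not describe the whole range.

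The primary effectiveness analysis and the 10-week cost-utility analysis, which is the primary economic result, are not touched. I class this as a cheap improvement.

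**What to change.** Replace the stopping sentence in section 12.4, item 2. Whatever the direction of the differences, item 2 should:

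- report incremental cost to the 5-week point and incremental ankle score, each with a bootstrapped 95% confidence interval;
- plot the bootstrapped cost-effectiveness plane and give the share of replicates in each quadrant;
- carry out the sensitivity analyses listed later in the section, including the one on the 3-10 day costs;
- omit only the ICER when one arm is dominant.

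The definition of dominance would then decide only whether the ratio is printed. An acceptability curve per ankle-score point is optional, because the protocol states no willingness-to-pay value per point.

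No new data are needed. The cost is a short wording change and a small amount of extra analysis and reporting for a secondary economic result: item 2 currently specifies the bootstrap only when no arm is dominant, so it would now be run in every case.
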